Salivary gland hypofunction and xerostomia are major complications following radiotherapy for head and neck cancer and may lead to debilitating oral disorders and impaired quality of life. Currently, only symptomatic treatment is available. However, mesenchymal stem cell (MSC) therapy has shown promising results in preclinical studies. Objectives are to assess safety and efficacy in a first-in-man trial on adipose-derived MSC-therapy (ASC) for radiation-induced xerostomia.

Methods

This is a single-center, phase I and II, randomized, placebo-controlled, double-blinded clinical trial. A total of 30 patients are randomized in a 1:1 ratio to receive ultrasound-guided, administered ASC or placebo to the submandibular glands. The primary outcome is safety. The secondary outcomes are efficacy, change in quality of life, qualitative and quantitative measurements of saliva, as well as submandibular gland size, vascularization, fibrosis, and secretory tissue evaluation based on contrast-induced magnetic resonance imaging (MRI) and core-needle-samples. The assessments are performed at baseline (one month prior to treatment), and one and four months following investigational intervention.

Discussion

The trial is the first attempt to evaluate the safety and efficacy of ASCs in patients with radiation-induced xerostomia. The results may provide evidence for the effectiveness of ASC therapy in patients with salivary gland hypofunction and xerostomia and deliver valuable information for the design of subsequent trials.

Trial registration section

EudraCT: 2014-004349-29. Registered: 1st of April 2015

ClinicalTrials.gov Identifier: NCT02513238. First received: 2nd of July, 2015

The trial is prospectively registered.

Key words

Mesenchymal stem cells, xerostomia

Background

Xerostomia is the term used for a subjective feeling of dry mouth. Xerostomia can be coexisting with or without a reduced secretion of saliva, although xerostomia is generally perceived only when unstimulated whole saliva flow rate is reduced by more than 40-50% [1]. Thus, a decreased (salivary gland hypofunction) or pathologically reduced saliva secretion (hyposalivation) will severely impact quality of life and may lead to dental decay. The three main causes of severe xerostomia and hyposalivation are adverse effects of medication intake (polypharmacy and/or xerogenic medications), Sjögren's syndrome and radiation therapy for head and neck cancer. With regards to cancer chemotherapy, studies suggest that in some patients it may induce temporary salivary gland hypofunction and xerostomia during and following treatment, while other patients are not affected to a noticeable extent, however, no firm conclusions can be drawn from the literature [2]. Radiation therapy plays a major role in the curative treatment of most head and neck cancers, either as a single modality, or in combination with chemotherapy, surgery, or both. Radiation therapy significantly increases local tumour control and chance of survival, but despite more advanced methods (intensity-modulated radiation therapy, IMRT), a significant proportion of the radiation is deposited in the normal tissue surrounding the tumour. The long-term effect of radiation on salivary gland tissue is deterioration of gland function. [3,4]. Salivary gland dysfunction after radiation therapy predisposes to a variety of undesirable conditions directly or indirectly as a result of decreased salivary flow rate as well as changed composition and increased viscosity of saliva and include xerostomia, impairment of oral functions due to insufficient wetting (i.e. speech, chewing and swallowing) and reduced lubrication of mucosal surfaces and of the ingested food. Furthermore, the oral mucosa is prone to frictional trauma and ulceration. In addition, a reduced salivary flow rate results in a reduced clearance of the oral cavity, thus leading to microbial overgrowth, which in addition to other factors may result in rampant dental caries, dental erosion and oral candidiasis [2,5].

The average total dose range which represents the threshold for a significant reduction in salivary flow rate is 26-39 Gray (Gy) [6–10]. The dose causing toxicity in 50% of individuals (TD 50) is likely to be approximately 40 Gy [11], which is similar to the TD 50 [12], estimated for submandibular hypofunction [13]. The used methods to reduce the incidence of xerostomia after radiation is prevention (including more advanced radiation techniques [IMRT or proton therapy], radio-protective agents [amifostine and tempol [14]], and the more recently proposed stem cell

sparing radiation therapy [15]).

A number of strategies to improve salivary gland function after radiation therapy have been developed, but all are symptomatic treatments only able to stimulate the function of the residual salivary gland tissue or provide short-term lubrication. These strategies include pharmacological agents, for example sialogogues (pilocarpine, cevimeline, etc), saliva stimulants (sugar-free, non-erosive lozenges, chewing gum and custom-made, non-erosive weak-acidic candy) [16], and the use of oral lubricants and saliva substitutes [17].

Stem cells have been identified as a potential treatment modality for a wide variety of cell degenerative disorders by virtue of their ability to differentiate into different specialized cell types. Most of the early work on stem cells has been performed in embryonic stem (ES) cells, which are derived from the inner cell mass of a blastocyst embryo. The clinical use of these cells as therapeutic agents is currently very limited, both due to histocompatibility problems and their potential ability to form malignant teratomas. Problems with histocompatibility have been improved with the development of induced pluripotent stem cells (iPS cells). In contrast to ES and iPS, which are both pluripotent stem cells i.e. ability to differentiate into cells deriving from all three primary germ layers, ecto-, meso-, and endoderm; adult stem cells are defined as multipotent, i.e. with a more narrow differential ability. In this respect, mesenchymal stem cells (MSCs) have gained considerable attention, since they are readily available from e.g. bone marrow and adipose tissue and have been characterized and investigated in a wide variety of pre-clinical studies and clinical trials.

Originally described more than 40 years ago, MSCs reside in almost all connective tissues [18]. More recently, there has been an increasing awareness that MSCs have a number of interesting secretory paracrine bystander characteristics including anti-inflammatory, anti-apoptotic, immunomodulatory, angiogenic and trophic (tissue-regenerating) properties. Notably, MSCs have shown promising results in preclinical studies for the treatment of xerostomia, including radiation-induced xerostomia [19].

The objectives of the current trial are to assess the safety and feasibility of autologous adipose tissue-derived MSCs administered for radiation-induced salivary gland hypofunction and

xerostomia in head and neck cancer patients. Head and neck cancer is the sixth most common malignancy worldwide, and the majority of these patients are due to advanced disease stage at presentation treated with chemo-, radiotherapy, or both [20,21]. The project can potentially help to develop a clinically relevant treatment option for the growing number of patients suffering from xerostomia after radiotherapy.

Methods and materials

Primary outcome

Primary outcome is safety, including adverse events (AEs) and severe adverse events (SAEs). All measures of AEs will be graded according to Common Terminology Criteria for Adverse Events (CTCAE) [22]. Since this is a local treatment with ASCs the primary safety measures are:

- Pain at injection site (Grade 1: Mild pain, grade 2: Moderate pain; limiting instrumental activities of daily living (ADL), grade 3: Severe pain; limiting self-care ADL)
- Oral discomfort (Grade 1: Mild discomfort; not interfering with oral intake, grade 2: Moderate pain; interfering with oral intake, 3: Disabling pain; tube feeding or total parental nutrition indicated)
- Infection (Grade 1: Localized; local intervention indicated, grade 2: Oral intervention indicated (antibiotic, antifungal, antiviral), grade 3: IV antibiotic, antifungal or antiviral indicated; or radiologic, endoscopic or operative intervention indicated, grade 4: life threatening consequences; urgent intervention needed)

Secondary outcomes

- Unstimulated and stimulated whole saliva and selective submandibular saliva flow rate and composition of saliva.
- Complaints of xerostomia as evaluated by a physician and patient questionnaire.
- Measurement of volume, fibrosis, and vascularisation change of submandibular glands based on magnetic resonance imaging (MRI).
- Morphological changes of the gland tissue, e.g. degree of atrophy, fibrosis, inflammation, and amount of specialized acinic cells including duct/acinic/myoepithelial cell ratio in histological sections from core-needle biopsies taken pre- (baseline) and post-interventional (4 months). An expert head and neck pathologist will be blinded to treatment of participants and evaluate the two sets of biopsies for changes.

Late complications – safety

To detect late complications or late adverse events all study participants, who received ASC-treatment are invited for a check-up one year and three years after treatment. Whether or not participants consent to a late check-up, the Principal Investigator ([name]) will contact participants by telephone to ensure that no subjective complaints have befallen. In case of subjective complaints, participants will be encouraged to meet for a physical examination.

Trial design

Randomized, placebo-controlled, phase I/II trial with double blinding (Figure 1, Figure 2, SPIRIT Checklist (Additional file 1)). All participants will undergo a mini lipo-suction from which ASCs will be ex vivo expanded in a good manufacturing practice (GMP)-approved clean room facility. The Good Clinical Practice committee performs data monitoring, and is independent from the sponsor and has no competing interests.

One month prior to the liposuction, participants will undergo a MRI scan of the submandibular glands, fill-out questionnaires on quality of life and undergo saliva measurements. Also, all patients will have blood samples analyzed for anti-HIV I/II, HBsAg, anti-HBc, anti-HCV and syphilis to fulfil the requirements in the Danish Tissue Act, as well as relevant kidney parameters to secure adequate renal function when using MRI contrast, see below. A core-needle-sample of one of the submandibular glands and a liposuction of the abdomen (approx. 60 ml of adipose tissue) are performed for all participants. Approximately 14 days following liposuction, participants will have ASCs or placebo injected in the submandibular glands on an outpatient basis. Subjects will subsequently undergo a saliva measurement, contrast-induced MRI and fill out questionnaires at baseline, 4 weeks post-intervention and 4 months post-intervention. Finally, at the 4-month visit, a small biopsy is taken from one of the two submandibular glands. The procedure takes place under local anaesthesia. Histology is determined (samples are blinded to the pathologist) (Figure 1).

Randomization

At inclusion to the study protocol, each participant will be given consecutive numbers starting with number 1. To randomize participants to either placebo or MSCs we will use a table of random numbers, generated by a computer program (<http://www.randomization.com>). This table with

randomization numbers will only be available to specified personnel at the Tissue Center, Department of Clinical Immunology (Rigshospitalet).

Amount of ASCs required for injection

Based on published animal studies the amount of cells given for xerostomia to mice varies from 2×10^5 to 2×10^6 [23]. To convert these mice data to a realistic dose in humans we have extrapolated numbers based on the following data: The volume density of submandibular glands very closely approximates 1 mg/mm^3 ($1.06\text{-}1.07 \text{ mg/mm}^3$) [24]. In the mice studies on radiotherapy the mean gland weight was approximately 350 mg, which corresponds to an approximate volume of 350 mm^3 . Accordingly, the mouse dose pr. gland volume is approximately 2.86×10^5 to $2.86 \times 10^6 \text{ ASC/cm}^3$ gland (when calculated from either 1×10^5 to 1×10^6). The volume of the submandibular gland in human subjects after radiotherapy is $6.6\text{-}7.9 \text{ cm}^3$ [25]. This corresponds to an approximate dose pr. patient of between 1.9×10^6 to 2.3×10^6 , or 1.9×10^7 to 2.3×10^7 cells pr. submandibular gland. From the above assumptions, and in order not to administer an inadequate number of cells, we have chosen to proceed with the maximum dose corresponding to $2.8 \times 10^6 \text{ ASC/cm}^3$ gland, i.e. a maximum total dose per patient of approximately $4.48 \times 10^7 \text{ ASCs}$ (see below). However, to standardize the dose administered to patients, the amount administered will be standardized to the size of their submandibular glands, as described below.

Injection of the ASCs or placebo-suspensions into submandibular glands will be performed by the principal investigator ([name]) under local anesthesia using ultrasonic guidance and sterile technique. The ASCs will be suspended in isotonic NaCl (0.9 mg/ml) and human albumin (HA) 1% to a final volume of 2 ml. Placebo will be 2 ml of isotonic NaCl (0.9 mg/ml) and HA 1%. After receiving the ASC-suspension or placebo-suspension, the surgeon (the principal investigator) will identify the submandibular glands and inject the ASC suspension. Calculation of injected number of ASCs pr. participant rests on the following calculation: $Suspension_{ml} = 2.8 \times 10^6 \frac{ASC}{cm^3} \times volume_{cm^3}$, where volume is the volume of the submandibular gland, and a gland-volume of approx. $7\text{-}8 \text{ cm}^3$ is the norm. Therefore, the amount of ASCs given to each participant will be approx. $2.8 \times 10^6 \frac{ASC}{cm^3} \times 8cm^3 \times 2 = 4.48 \times 10^6 \text{ ASCs}$ in total. If the expanded number of ASCs does not fulfil the above criteria, it is accepted to diminish the number to a minimum of 50% of the calculated dose.

Justification for patient population

In order to standardize the participant population, we choose to only include participants treated for a human papilloma virus (HPV)-positive oropharyngeal squamous cell carcinoma, and exclude patients with severe salivary gland hypofunction and already manifest or near-manifest xerostomia, as this population most likely will not benefit from this treatment. This will be assessed by a preliminary questionnaire and a subsequent saliva flow rate measurement before inclusion.

Eligibility criteria

Evaluation of eligibility criterias and consent forms are collected by the Primary Investigator.

Inclusion criteria:

- Previous radiotherapy for a T1-T2 and N0, N1 or N2a, HPV-positive oropharyngeal squamous cell carcinoma with bilateral irradiation of the neck
- 2 years follow-up without recurrence
- Clinically reduced salivation and hyposalivation, evaluated by a screening
 - Unstimulated whole saliva flow rate in the range of 0.05-0.20 ml/min
- Informed consent
- Grade 1-3 xerostomia as evaluated by the “Udvalg for Kliniske Undersøgelser” (UKU) side effect rating scale[26].

Exclusion criteria:

- Any cancer in the previous 2 years
- Ongoing xerogenic medications
- Any other diseases of the salivary glands, e.g. Sjögrens syndrome, sialolithiasis, etc.
- Pregnancy or planned pregnancy within the next 2 years
- Breastfeeding
- Any other disease/condition judged by the investigator to be grounds for exclusion
- Treatment with anticoagulant that cannot be stopped during the intervention period
- Failure of expanding up to 50% of the calculated dose of ASC
- Withdrawal of informed consent

Criteria for withdrawal of subjects under study

- Pregnancy
- Infection of the transplanted site
- Allergy to local anesthetic
- Withdrawal of consent from participants
- In case of withdrawal or dropouts before assessment of efficacy patients will be replaced to ensure that a total of 30 patients complete the study.

Surgical method for mini-liposuction

The procedure is done in an outpatient setting, and performed under sterile conditions according to local guidelines. 6 ml of local anesthesia (lidocaine 1 %) is injected subcutaneously at two injection sites of the lateral abdomen. Two 5 mm incisions are then made and Klein's solution is injected with a blunt infiltrator through the incisions. The fatty tissue is harvested from the abdomen with a 3 mm blunt cannula 23 cm in length, coupled to the MonoJect 60 ml syringe with a blunt and Toomey tip (Teico Healthcare). The harvested lipoaspirate is sedimented in the syringe. Any oil layer at the top or aqueous layer at the bottom is removed. By this procedure the middle layer of fat tissue is obtained and will be transported in a sterile plastic bag for the isolation of ASCs.

Surgical method for submandibular gland biopsy

This procedure takes place in an outpatient settings. A biopsy will be taken 14 days before injecting the ASC and four months after injection. The biopsy procedure is carried out under sterile conditions; in local anesthesia with lidocaine with epinephrine 0.5% an ultra-sound-guided, core biopsy of one of the glands is taken. Participants are randomized for biopsy of either the right or left gland. Each biopsy will be fixed in 4% formalin and sent for histology.

Surgical method for injection of ASC or placebo in submandibular gland

The procedure will be performed without local anesthesia in an outpatient setting. The surgeon will receive two syringes of the sterile ASC-suspension or placebo of each 1 ml (total of 2 ml). The suspensions are injected into each submandibular gland guided by ultrasound. The ASC-suspension will be deposited in two areas (superficial and deep lobe) with equal volume per site (0.5ml) to ensure equal distribution of the suspension. The subject will afterwards receive a small band aid,

which can be removed the same day. The participant will be administered over the counter pain relief.

Assessment of xerostomia and subjective treatment outcome

The subjective effect of the treatment is assessed by a 100 mm visual analogue scale of xerostomia filled out by the patient [27] and a physician-rated questionnaire [28], both carried out at baseline as well as one and four month after treatment (Figure 1).

Assessment of salivary flow rate and objective treatment outcome

Changes in the secretion rate of the unstimulated whole saliva in the oral cavity is probably the most important parameter for the biological development of xerostomia and accompanying pathological oral conditions. Whole saliva, e.g., the secretions from the major and minor salivary glands are mixed in the oral cavity. A precise determination of this value is crucial for the assessment of efficacy in this trial. For determination of the saliva flow rate, whole saliva will be collected between 2 p.m. and 3 p.m. for all collections to take the salivary diurnal variation into account. Participants will refrain from eating, drinking, smoking and oral hygiene for 2 hrs. prior to collection. After being seated upright in a chair, subjects relax for 5 min and are then instructed to make as few movements as possible, including swallowing, during the collection.

At baseline, one and four months after treatment, unstimulated whole saliva will be collected using the spitting method [29] where participants spit their saliva into a collection container over a period of 15 minutes. The salivary flow rate (SFR) (ml/min) is determined as the increase in weight of the container divided by the collection time in minutes. After the collection of unstimulated saliva, the subjects are instructed to chew on 1 g of sterile paraffin wax. Participants will chew for 60 s, and clear the oral cavity for saliva. Subsequently, as the glands are now in a stimulated state, participants will continue chewing the paraffin wax and expectorate into a saliva collector for the duration of five minutes. Subsequently, testing of the submandibular glands will be performed. To assess ASC efficacy on the submandibular glands, saliva is also collected directly from the floor of the mouth in an unstimulated and stimulated state. The flow rate of the submandibular glands will be assessed by the swab method with cotton rolls placed buccally in each maxillary molar region to block the orifices of the parotid ducts and cotton rolls under the tongue in the floor of the mouth to collect submandibular/sublingual saliva. Immediately prior to the start of collection participants will be asked to swallow. Unstimulated saliva testing will be performed with neutral

cotton rolls(Salivette ®, Sarstedt, Nümbrecht, Germany) and stimulated saliva testing with cotton rolls with 20 mg citric acid (Salivette with citric acid ®, Sarstedt, Nümbrecht, Germany). For both measurements, collections takes place during a period of 3 min. Saliva flow rates are determined by weight (1 g equals 1 ml of saliva) with cotton rolls weighed before collection and reweighed after. The flow rates are calculated as the increase in weight during collection and expressed as millilitres per minute. Saliva from the cotton rolls will be extracted by centrifugation (1500 g) and analyzed for its composition. From each of these collections, saliva will be aliquoted and stored at -80°C.

Chemical analysis of saliva

Whole saliva contains a large number of bacteria and epithelial cells, as well as gingival crevicular fluid. Therefore, whole saliva is normally not suited for the analysis of sensitive chemical parameters. For this purpose, non-contaminated selectively collected saliva from individual glands: i.e. parotid and submandibular/sublingual saliva is more suitable. The following analyzes will be performed on the collected saliva: pH and bicarbonate by ionic balance estimation [30], sodium, potassium, calcium, phosphate, chloride and fluoride [16], total protein, selected proteins [31] and amylase [32]. Chemical analysis will provide an estimate of dental and mucosal protective capacity of the saliva before and after treatment.

MRI analysis of the submandibular glands

A 3.0-Tesla 4-channel head coil and a dual-channel neck coil are employed to obtain hsMRI images of subjects (Siemens Magnetom Verio; Erlangen, Germany).

Volumetric and tissue-specific analysis will be performed based on axial and coronal sequences with 72 slices and 4-mm slice thickness including diffusion weighted and dynamic contrast-induced sequences. The contrast agent used is Gadolinium (“Gadovist”).

Statistical analyses

Data will be analyzed with SPSS v. 24 (IBM) or R statistics. We will use Excel or Access databases for collecting and entering data. All data will be double-entered. End of trial is defined as: last patient’s last visit (LPLV).

The results on salivary flow rate will be calculated as a percentage change in salivary flow rate (from baseline) in the group of participants given ASCs compared to the change-score in the control group.

Histologically, the composition of glandular tissue in the submandibular gland will be calculated

from before (baseline) and four months after the intervention (Figure 1). The differences between the intervention and the placebo group will be calculated by a non-paired t-test, alternatively a non-parametric test, if the conditions for parametric tests are not present. Differences are considered statistically significant if the two-sided p-value is less than 0.05.

Sample size calculation

The following sample size determination is based on a non-paired t-test. The minimal change in salivary flow rate that we want to be able to determine is 50%.

Standard deviation (SD) of a salivary flow rate measurement can, using the spitting method in healthy participants and under completely standardized conditions, be minimized to about 20%. The SD can vary greatly and we have, therefore, in this test used a value from the published literature [33] for persons with reduced unstimulated whole salivary flow rate (from 0.00 to 0.20 ml/min) and/or hyposalivation (< 0.10 mL/min) indicating a relative SD of 58% of these groups. However, since we are interested in a comparison of change scores (change from baseline to after treatment) between the intervention and placebo group we apply the rule of thumb that the SD of the change score equals $SD/2^{0.5}$, which equals an SD of approximately 41%. The power is set at $(1-\beta)$: 90%. Significance level (α) is set at 0.05. This is a trial with a continuous response variable from independent control and experimental research unit with one control per experimental research unit. If the true difference in the change score between experimental and control means is 50%, we will need to study 15 participants for the experimental intervention and 15 patients as control population in order to reject the null hypothesis that the population means of the experimental and control groups are equal with a study power of 90%. The Type I error probability associated with this test of this null hypothesis is 0.05.

All investigators will have access to the final trial dataset.

Discussion

This first-in-man trial aims to establish the safety, efficacy and feasibility of autologous, adipose-derived stem cell therapy for patients with radiation-induced xerostomia. In addition, it provides an opportunity to advance trial methodology for the assessment of the putative role of stem cell therapy and provide suggestions for the design of subsequent trials to verify potential efficacy. To establish safety profile of the intervention, selection and timing of appropriate outcomes have been guided by similar intervention studies [34], and our trial design facilitates conditions for assessment

of short and long-term changes and complications.

We have strived to standardize saliva testing by performing tests at the same time of the day, and instructed and supervised by the same person ([name]). All participants are fasting two hours before the testing. This period is deemed useful to exclude any stimulants (e.g. lunch and drinking liquid) before testing, but might especially for participants with hyposalivation (e.g. participants with unstimulated whole saliva flow rate ≤ 0.10 ml/min) induce almost no secretion. Further, we perform in total four saliva measurements per visit (two tests for whole saliva (unstimulated/stimulated), and two tests for the submandibular glands (unstimulated/stimulated)) totaling to an effective period of 26 minutes of saliva testing. This is possibly too extensive for some participants meaning that the glands will when testing the submandibular glands not be capable of further secretion. Testing of the submandibular glands is performed following the stimulated testing of all glands (whole saliva). It might be an advantage to test the submandibular glands in a post-stimulated state, but it should be noted that the glands are stimulated. Testing of the submandibular glands is performed by placement of cotton rolls at the orifices under the tongue, and consequently the rolls will also collect saliva from the sublingual glands.

We have adjusted numbers of cell according to gland size based on experience from preclinical studies, but whether this is transferable to humans, and the dose is adequate remains unknown.

Following the liposuction 12-14 days prior to treatment, a core-needle biopsy of one of the submandibular glands (participants are randomized for biopsy of either the right or left gland) is performed. It cannot be excluded out that this procedure might inflict salivation and influence the effect of the ASCs. It is well-documented that ASCs secrete bioactive molecules that provide a regenerative microenvironment for a variety of injured tissues to limit damage and facilitate a regenerative response[35]. In this context, it is unknown whether injection to the submandibular glands regenerates only damaged tissue from the biopsy or also generates new or improved tissue.

In connection with the injection of the MSCs into the salivary glands, there is a minimal risk of adverse events, such as pain, infection and bleeding. The risk of these adverse events is less than 0.5% using similar procedures. A theoretical risk of a possible carcinogenic effect in the treatment of MSC has been discussed due to their production of growth factors such as epidermal growth factor (EGF). These considerations are particularly relevant, since MSCs are used in participants previously diagnosed with cancer. However in model systems of cancer, the effect of MSCs on

cancer growth is controversial as they have both been shown to be inhibitory and stimulatory [36,37]. Vascular endothelial growth factor (VEGF) is a known facilitator of angiogenesis, and might be a mediator of the potential effect of ASCs[38].

Based on numerous trials including studies with local injection of MSCs with a total of more than 1,000 participants with MSCs in and no increase in the incidence of cancer is detected [39,40]. Data on ex vivo expanded MSCs have not, despite extensive research, indicated malignant transformation [41], including a study that demonstrated that the injection of a very high dose of ASC (240×10^6 MSC/kg) revealed no signs of cancer, organ toxicity or change in body-weight after 12 months in mice [42].

It is estimated that the risks of adverse events in the experiment is outweighed by the benefits of participation. If the treatment has a clinically significant effect and is safe, patients suffering from radiation-induced xerostomia could be offered a simple, minimally invasive procedure with few adverse events and risks, which is in contrast to the current sub-optimal treatments.

Trial status

This is an investigator-initiated phase 1/2 trial funded by the Candy's Foundation. The ethics committees have given full approval. Date of first enrollment was 22th May 2015. The trial is in the recruitment phase.

Abbreviations

Mesenchymal stem cell (MSC)

Intensity-modulated radiation therapy (IMRT)

adipose-derived MSC-therapy (ASC)

magnetic resonance imaging (MRI)

epidermal growth factor (EGF)

Vascular endothelial growth factor (VEGF)

Standard deviation (SD)

milliliter (mL)

Kilogram (kg)

last patient's last visit (LPLV).

Declarations

Ethical Approval and Consent to participate

Ethics approval (The Danish National Board): 1406653

We have obtained informed consent from all participants in the study.

Consent for publication

Not applicable

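### The worked dose line gives a participant total of 4.48×10^6 cells, but its own factors multiply to 4.48×10^7

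*Combined protocol and SAP*

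**What the plan says.** All the dosing text is in the section Amount of ASCs required for injection.

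- **First paragraph.** The chosen density is 2.8×10^6 cells per cm³ of gland, "i.e. a maximum total dose per patient of approximately" 4.48×10^7 cells, with a pointer to the text that follows. It adds that "the amount administered will be standardized to the size of their submandibular glands". For the size of one gland it says: "The volume of the submandibular gland in human subjects after radiotherapy is" 6.6 to 7.9 cm³.
- **Second paragraph, formula.** "Calculation of injected number of ASCs pr. participant rests on the following calculation": a left side labelled as suspension in ml, set equal to 2.8×10^6 cells per cm³ times volume in cm³, "where volume is the volume of the submandibular gland". A gland of about 7 to 8 cm³ is called normal.
- **Second paragraph, worked line.** "Therefore, the amount of ASCs given to each participant will be approx" 2.8×10^6 × 8 × 2, printed as equal to 4.48×10^6 cells in total.
- **Second paragraph, minimum dose.** If expansion falls short, "it is accepted to diminish the number to a minimum of 50% of the calculated dose". The exclusion criteria carry the matching rule: "Failure of expanding up to 50% of the calculated dose of ASC".

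The injected volume is fixed at 2 ml, here and under Surgical method for injection of ASC or placebo in submandibular gland, where it is two syringes of 1 ml.

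**The concern.** Two consecutive paragraphs give totals for the same dose that differ by a factor of ten. The wrong one is in the paragraph that tells staff how to work out the dose.

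The printed total does not look absurd. The first paragraph also quotes a low range from the animal work, 1.9×10^6 to 2.3×10^6 cells. Doubled for two glands, that is 3.8×10^6 to 4.6×10^6, and 4.48×10^6 falls inside it. A reader who took the total without multiplying the factors could believe that the low dose was intended, although the plan chose the maximum.

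The calculated dose also drives two decisions: whether a reduced product may be injected, and whether a participant is excluded for failed expansion. A reader who took half of the printed total at 8 cm³ per gland would accept a product with 5% of the intended cells (2.24×10^6 / 4.48×10^7).

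**Working it through.** **Inputs**, all from Amount of ASCs required for injection: density 2.8×10^6 cells/cm³; 8 cm³ per gland in the worked line (7 to 8 cm³ called normal); 6.6 to 7.9 cm³ per gland after radiotherapy; two glands; minimum 50%.

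**Formula.** Cells per gland = density × gland volume. Participant total = sum over the two glands.

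**1. The total in the first paragraph.** 2.8×10^6 × 8 = 2.24×10^7 per gland; × 2 = 4.48×10^7. This reproduces the stated maximum.

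**2. The total in the worked line.** The same factors are printed as 4.48×10^6. Ratio: 4.48×10^7 / 4.48×10^6 = 10. Not reproduced.

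**3. Does any volume in the plan give the printed figure?**

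| Volume per gland | One gland | Two equal glands | 50% of total |
|---|---|---|---|
| 6.6 cm³ | 1.85×10^7 | 3.70×10^7 | 1.85×10^7 |
| 7 cm³ | 1.96×10^7 | 3.92×10^7 | 1.96×10^7 |
| 7.9 cm³ | 2.21×10^7 | 4.42×10^7 | 2.21×10^7 |
| 8 cm³ | 2.24×10^7 | 4.48×10^7 | 2.24×10^7 |

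None does. Working back, 4.48×10^6 / (8 × 2) = 2.8×10^5 cells/cm³. That is about the low end of the animal range (2.86×10^5), not the density chosen.

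**4. Cross-check with the per-gland range.** The first paragraph's upper range is 1.9×10^7 to 2.3×10^7 cells per gland, from 2.86×10^6 × 6.6 = 1.89×10^7 and 2.86×10^6 × 7.9 = 2.26×10^7. The 2.24×10^7 per gland from step 1 lies within it. The printed total would allow only 4.48×10^6 / 2 = 2.24×10^6 per gland.

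**5. Units of the formula.** cells/cm³ × cm³ = cells. The right side is a cell count for one gland, while the left side is labelled in ml and the sentence introduces it as a number per participant. The factor of two appears only in the worked line.

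**6. The maximum.** Two glands of 8 cm³ reach 4.48×10^7 exactly. Two glands of 9 cm³ (an assumed size, for illustration) would give 2.8×10^6 × 18 = 5.04×10^7, above the stated maximum. The plan does not say which of the two then governs.

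**The case against.** The strongest case against is that this is one wrong character which the text itself corrects. The first paragraph has the right total and points forward to the line, the per-gland range agrees with it, and the line prints all three factors. It is also an approximate illustration at a typical volume; the rule itself is density times volume. All of that is true, and it is why the intended dose can be recovered. It does not make the printed total right, and a worked total in operative dosing text is a figure that people use.

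The text examined was extracted from a PDF, so a misread exponent cannot be excluded. The exponent for the same total came through as 7 in the first paragraph, but that does not settle it. If the original shows 10^7 in the worked line, only the label and the question about the maximum remain.

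A reader might infer more, and the documents do not support it:

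- **That the ml and per-participant labels make the rule unusable.** They are loose notation. The injected volume is fixed at 2 ml in two places, and the next sentence supplies the doubling.
- **That the plan doubles one gland and ignores a difference between the two.** The doubling is in an example at a typical volume. The formula applied to each gland gives left plus right, which fits the plural in "the amount administered will be standardized to the size of their submandibular glands". What is missing is one explicit sentence.
- **That the 50% minimum is a fixed cell number, or inherits the wrong total.** Both rules refer to the calculated dose, which is specific to the participant. Anyone who multiplies the factors gets the right minimum.

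**Conclusion.** The point holds. As written, the participant total in the worked line is ten times too low: 4.48×10^6 printed, against 4.48×10^7 from its own factors and from the preceding paragraph. At 8 cm³ per gland the minimum acceptable dose is 2.24×10^7 cells, not 2.24×10^6. Across the post-radiotherapy gland volumes that the plan cites, and assuming equal glands, the total runs from 3.70×10^7 to 4.42×10^7 and the minimum from 1.85×10^7 to 2.21×10^7.

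It would be tempting to conclude that participants were, or would have been, given a tenth of the intended dose. Nothing in the documents shows that: the density, the volumes and the correct total are all stated, and there is no record of doses given. Nor does the error reach the statistics. The sample size rests on salivary flow rate, and no planned analysis uses the cell count.

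The conclusion assumes that the exponent was extracted correctly and that the chosen density is 2.8×10^6 cells/cm³, as both paragraphs state. The mislabelled formula and the unclear status of the maximum are smaller matters that can be settled in the same edit.

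**What to change.** In the second paragraph of Amount of ASCs required for injection:

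1. Check the original document and, if it also shows 10^6, change the worked total from 4.48×10^6 to 4.48×10^7.
2. Relabel the left side of the formula from suspension in ml to *number of ASCs per gland*, and state that the participant total is the sum over the two glands.
3. Leave the maximum in the first paragraph as stated, and ask the sponsor to confirm whether it caps the dose when the glands are larger than 8 cm³. If it does, say so next to the formula.

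The 50% rule and the exclusion criterion need no new number; both follow the corrected calculation. Items 1 and 2 are wording only, and item 3 needs one answer from the sponsor. The design, the analysis and the sample size do not change, and items 1 and 2 leave the intended dose as it is.
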